This pilot study plans to recruit about 50 patient/caregiver — oncologist dyads. The recruitment process contains three stages. First, medical oncologists who are currently in clinical practice at participating institutions and care for patients with solid tumors will be approached. Second, participating oncologists' patients will be recruited if they are: (1) currently a patient of a participating oncologist, (2) diagnosed with stage III or IV solid cancer, (3) aged 20 years or older, (4) able to tolerate an interview that will last approximately 30 minus, and (5) able to speak Chinese or Taiwanese. Finally, if applicable, adult caregivers who intent to join selected out-patient-department (OPD) visit with the patients will also be recruited.

Research Design

This is a mixed-methods study with a two-phase exploratory sequential design. The first phase is a qualitative descriptive study in which we will record patient/caregiver—oncologist OPD visits and conduct patient/caregiver interviews to address aim 1 and 2. Discourse and conversation analysis will be used to analyze the recorded visits and content analysis will be used to analyze the interviews. The second phase is a correlational study in which we use questionnaires to measure variables and examine their relationship with interaction patterns (aim 3). Descriptive statistics, binomial logistic regression, and linear regression will be used to analyze quantitative data.

Expecting Results

This is a pioneering study addressing the patterns and associating factors of symptom communication in Taiwanese patients with advanced cancer. Our findings will systematically map out the patient/caregiver—provider symptom communication and identify relationships between communication patterns and meaningful indicators. This proposed study is a critical step to understand patient/caregiver—provider communication regarding symptoms in order to pinpoint symptom management and communication barriers and design proper interventions in Taiwan.

Key words: Health communication, Symptom management, Mixed-methods design, Cancer Care, Advanced cancer

Background

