While the proposed study does not intend to test the whole theory, specific aim three was informed by the Dual Process Theory of Supportive Message (DPT). DPT was firstly published by Burlison in 2008 with the main purpose of providing a systematic explanation about factors affecting communication and its outcomes (25). One of the important assumptions proposed by the DPT is: communicators' ability to handle the message (A) and their motivation (M) to discuss the topics mediates the relationship between quality of communication (Q) and communication outcomes (O). In the proposed study, we conceptualize the 'ability to handle the message' as **patients' perceived ability to communicate with providers** and 'motivation' as **symptom severity**. That is, we propose to explore the relationship between **TIPSC (Q)**, **patients' perceived ability to communicate with providers (A)**, **symptom severity (M)**, **congruence in symptom assessment between patients and providers (O)**, and **patient satisfaction (O)**. Figure 1 shows the modified conceptual framework.

[figure not shown]

Figure 1. Modified Conceptual Framework of Dual Process Theory of Supportive Message

Table 1. Interaction Patterns, Defining Characteristics, and Exemplars

Interaction pattern	Defining characteristics	Exemplars [O] Oncologist, [P] Patient, [C] Caregiver

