Aim 1. Validating a newly established typology regarding interaction patterns of unstructured symptom discussion in Taiwanese advanced cancer population.

Aim 2: Exploring patients’ experience and thoughts of symptom discussion in regard to their interaction patterns and symptom experience.

Aim 3: Examine relationships between interaction patterns and (a) demographic variables, (b) symptom severity, (c) congruence in symptom assessment between patients/caregivers and providers, (d) patients’/caregivers’ perceived ability to communicate with providers, and (e) patient/caregiver satisfaction.

Procedures

- Recruiting oncologists, patients, and caregivers (collecting demographic information and scheduling an out-patient-department (OPD) visit to be recorded)
- Record 1 OPD visit
- Collect quantitative data: questionnaire measurements
- Schedule an 30-40 minutes interview
- Interview (Incentive will be provided after the interview)
- Analyze the recorded office visit using discourse and conversational analysis: determining interaction patterns
- Analyze the interview using content analysis: exploring patients’ experience regarding the recorded symptom communication
- Analyze quantitative data: the relationship between identified interaction patterns and questionnaire measurements
- Triangulation: compare the results from qualitative interview with the quantitative data to see how the data support or disagree with each other
- Drafting preliminary research report

Figure 2. Research Schema: Conceptual Underpinnings, Study Phases, and Corresponding Specific Aims and Procedures

Methods and Procedures

The method section describes sampling process and study methods of each phase.

Sampling. Because a qualitative study typically requires about 30-50 participants (28), the sample size of this pilot study is set to be 50. The two samples of phase one and two will include the exactly same individuals and same sample size which is about **50 patient/caregiver—physician dyads**, including about 50 patients, 10 physicians, and 50 caregivers, if applicable.

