There are three steps of recruitment processes. First, physicians who are currently in clinical practice at National Taiwan University Hospital and care for patients with solid tumors will be recruited through study presentations at grand rounds, meetings, or personal contacts. A research assistant then meets with interested physicians for explaining the details of the study, consenting, and setting up following schedules for recruiting patients at OPD visits. Second, research assistants identify potential eligible patients by working closely with participating physicians and their clinic nurses. These potential eligible patients will be approached by their physicians, nurses, or research assistants. We include patients who are: (1) currently a patient of a participating physician, (2) diagnosed with advanced solid cancer (TNM stage III or IV), (3) aged 20 years or older, (4) able to tolerate an interview that will last approximately 30 minutes, and (5) able to speak Chinese or Taiwanese. Patients who (1) do not experience any symptoms, or (2) are hospitalized at recruitment are excluded. Finally, caregivers who will participate in the OPD visits with participating patient will be approached. Caregivers who are younger than 20 years old or cannot speak Chinese or Taiwanese will be excluded.

Recruitment process. Interested patients and their caregivers will receive a pamphlet regarding study information when research assistants explain study process, confirm participation, and arrange schedules. Signed written consents will be obtained from physicians, patients, and caregivers before data collection. Participated patients and caregivers are required to (1) provide an audio-recorded, unstructured OPD visit with their physicians, (2) complete 3 survey measurements (European Organization for Research and Treatment of Cancer, Perceived Efficacy in Patient-Physician Interactions scale, and The Chinese Patients' Satisfaction Scale), and (3) participate in a 30-40 minutes interview at home or a private room. On the other hand, participated physicians will complete European Organization for Research and Treatment of Cancer immediately after the recorded OPD visit. Figure 3 represents the recruitment and data collection process.

[figure not shown]

Fig 3. Recruitment and Data Collection Process

Table 2. Example Interview Guide (Patient version)

*[] 中文字會視每位病人在診間與醫師的對話內容而更動

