Conversation analysis (CA) and discourse analysis (DA) will be used to analyze the transcripts of audio-recorded, naturally occurring OPD conversations as we want to understand patterns of symptom communication and verify the TIPSC (aim 1). CA and DA are selected because they allow us to focus on naturally occurring conversation and what is being accomplished in conversations (29-31). Particularly, CA considers talk-in-interaction as a co-constructive and collaborative process, which fits more with patient-centered and relationship-centered approaches to medical communication (32). CA and DA share similar assumptions and are firstly developed in sociology and linguistics before rapidly evolving in a wide range of disciplines including psychology and social medicine (31). While CA will provide analytic tools to (1) examine the talk turn by turn and (2) look for the related features of patient-provider symptom communication which is a unique sub-type of medical communication (33-36), Goodman's (2017) eight steps of conducting DA will guide the analysis steps of the current study.

Step 1: Deciding Appropriate Research Question. The researchers will focus on aim one which is appropriate for CA/DA because of its action-orientation.

Step 2: Picking Appropriated Data Source. The researchers will analyze naturally occurring OPD conversations which are idea for CA/DA as they are interaction-based.

Step 3: Generating a Corpus. 'Corpus' means 'the collection of all the appropriate data that will be analyzed.' While the researchers plan to record one OPD visit for 50 patient/caregiver—physician dyads, only conversations which contain discussions of symptoms will be included and analyzed.

Step 4: Transcribing Data. The data are primarily transcribed according to the conventions developed by Jefferson (37, 38), with slight modifications to those inapplicable to Mandarin Chinese characters. Jefferson's transcription conventions make it possible to capture the details of the talk—not only what was said, but also the way it is said. Pauses, rising/lower volume, or the change of intonation will be noted. Remarks on other verbal sounds—such as coughing and clearing throat—will be provided in italics inside double parentheses. The following software will be used to assist data transcription: Speechnotes, ELAN, and InqScribe.

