Step 5: Preliminary Reading of the Data. The researchers will immerse themselves in the data and begin the first round of analysis including writing down initial thoughts about the data and categorize interactions into different patterns based on TIPSC. NVivo qualitative data analysis

software (version 11.4.1; QSR International Pty Ltd, 2017) and Microsoft Word will be used to aid the analysis

Step 6: Generating Results. The researchers use specific strategies or ‘discursive devices’ to enhance the analysis. Specifically, the researchers explore the following characteristics of each interaction type of TIPSC: turn-taking organization, sequence organization, and turn design (34, 35, 39, 40). These interrelated characteristics reflect different dimensions of patient-provider communication. First, we will examine how participants take turns and whether the interaction uses a special turn-taking organization. Looking at turn-taking, we will by default locally deal with pauses, overlaps, and interruptions. We will also, on overall level, explore whether the turns are equally distributed throughout the OPD visits by considering turn length and turn composition. For example, the interaction pattern identified as ‘agentic’ refers to the interaction in which patients and/or caregivers are particularly vocal during discussions, taking longer and complex turns; the pattern ‘checklist’ is organized by question-answer turn-taking organization with providers asking a series of questions in rote fashion. Second, with a focus on sequence organization, we will look at how particular courses of action are initiated and negotiated in sequences. Then, we will look at the turn design: how a turn is designed to perform certain action and how the turn is composed. That is, what the turns are doing and what linguistic elements, both syntactically and lexically, are selected to embody the actions. Lexical choice particularly draws researchers’ attention in prior research (41). Here we provide a data set from Heritage et al. (2007) to demonstrate the three dimensions turn by turn analysis.

01 DOC: -> And do you have any other medical problems?
 02 PAT: Uh No
 03 (7 s of silence)
 04 DOC: -> No heart disease?
 05 PAT: ((cough)) No.
 06 (1 s of silence)
 07 DOC: -> Any lung disease as far as you know?
 08 PAT: No.

(Heritage et al., 2007: 1430)

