Patients' perceived ability to communicate with providers will be measured by **Perceived Efficacy in Patient-Physician Interactions Scales (PEPPI-10, Chinese version)**. PEPPI-10 is a self-evaluated, 10-item instrument measuring patients' self-efficacy in "obtaining medical information and attention to their medical concerns from physicians (46)." Patients rate their confidence of interacting with physicians (e.g., get a doctor to pay attention to what you have to say) from "no confident (0)" to "extremely confident (10)". The Chinese version of PEPPI-10 shows good validity and reliability with the reported Cronbach's α coefficient of 0.907 (47).

Patients' overall satisfaction will be measured by the **Chinese Patients' Satisfaction Scale (C-PSS)**. C-PSS is a 27-item instrument which was developed to measure Chinese patients' satisfaction using a 5-point Likert scale. Patients rate their satisfaction from strongly disagree (1) to strongly agree (5) with higher scores represent better satisfaction. It is a reliable and valid tool with the reported Cronbach's alpha coefficient of all dimensions above 0.90 (48).

The major interaction patterns or combination of interaction patterns will be determined and dummy coded. Binomial Logistic Regression will be used to examine the relationship between interaction patterns and dichotomous variables (i.e., the congruence of symptom reports) while Linear Regression will be applied to examine the relationship between the interaction patterns and other variables, such as age, level of symptom severity, perceived communication ability, and satisfaction. The SPSS software will be used to organize the data and facilitate data analysis. Finally, combining and comparing the findings from the interviews and the results from the quantitative measurements enable us to do triangulation to fully map up the interaction behavior pertinent to symptom discussion.

Trustworthiness

To ensure the quality of study results and conclusions, five standards outlined by Miles and colleagues (2013) will serve as an evaluative framework. The standards are **confirmability, reliability, credibility, transferability, and utilization**.

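### Aim 3 regressions carry no physician term although about 50 patients come from about 10 physicians, so physician differences can be read as interaction-pattern effects

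*Combined protocol and SAP*

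**What the plan says.** The Sampling paragraph plans a sample "including about 50 patients, 10 physicians, and 50 caregivers, if applicable". A patient qualifies only if "currently a patient of a participating physician", so nesting of patients within physicians is built into recruitment.

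The analysis paragraph of Phase 2 says that "The major interaction patterns or combination of interaction patterns will be determined and dummy coded". It then assigns binomial logistic regression to congruence of symptom reports, and for the rest says that "Linear Regression will be applied to examine the relationship between the interaction patterns and other variables", naming age, symptom severity, perceived communication ability and satisfaction. The Abstract matches: "Descriptive statistics, binomial logistic regression, and linear regression will be used to analyze quantitative data". No section mentions a physician effect, clustering, a multilevel model or cluster-robust errors. Oncologists' demographic data are collected, but no model is said to use them.

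**The concern.** Ordinary regression treats the 50 patients as independent. Here the explanatory variable is itself partly physician behaviour. Step 6 of Phase 1 describes the *checklist* pattern through "providers asking a series of questions in rote fashion". It is not only that: *agentic* is defined by the patient or caregiver, and the plan notes that "CA considers talk-in-interaction as a co-constructive and collaborative process". How far a physician keeps to one pattern is therefore unknown.

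Two things follow if physicians do so to some degree:

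- **Confounding.** If physicians with different habits also differ in how satisfied or confident their patients are, the pattern coefficient absorbs that difference.
- **Standard errors.** If scores cluster by physician for any reason, p-values may be modestly too small.

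The Conceptual Underpinnings section labels pattern as communication quality and satisfaction as a communication outcome, so a physician difference could be reported as going with the pattern. The Expecting Results section intends to use the estimates to size larger studies, so a false difference would carry forward. Such studies would probably also recruit through physicians and need an ICC, which this plan does not ask for.

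**Working it through.** **Inputs from the plan.** About 50 patients and 10 physicians, so 50/10 = 5 patients per physician; patterns dummy coded. The figure of 50 comes from a qualitative convention, so there is no sample-size calculation to reproduce. No significance level, power or ICC is stated.

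**Assumptions.** Two-sided 5% test; outcome ICC 0 to 0.3; one pattern per visit; habitual share *s* (the share of a physician's visits in his or her usual pattern) 50% to 90%; gap *g* between two groups of physicians 0.2 or 0.5 SD.

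**1. Confounding.** Take two patterns, five physicians mainly using A, five mainly using B, and no true pattern effect. A fraction *s* of A visits, and 1 − *s* of B visits, come from the A-habit physicians. The expected difference from ordinary regression is therefore

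g·s − g·(1 − s) = g(2s − 1).

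For g = 0.5 this is 0.10, 0.20, 0.30 and 0.40 SD at shares of 60, 70, 80 and 90%. For g = 0.2 and s = 0.7 it is 0.2 × 0.4 = 0.08 SD.

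Simulation with g = 0.5 (remaining physician variance 0.1, within-physician variance 0.9, 4,000 runs):

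| Share | Ordinary: estimate (rejects) | Random intercept: estimate | Fixed effects: estimate (rejects) | SE ratio, fixed/ordinary | Single-pattern physicians |
|---|---|---|---|---|---|
| 60% | 0.105 (6.4%) | 0.062 | 0.003 (4.7%) | 1.04 | 8.7% |
| 70% | 0.206 (12.0%) | 0.133 | 0.009 (5.2%) | 1.11 | 16.9% |
| 80% | 0.305 (19.8%) | 0.216 | 0.000 (4.5%) | 1.25 | 32.9% |
| 90% | 0.412 (32.1%) | 0.339 | 0.013 (5.3%) | 1.70 | 58.8% |

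The last column agrees with s⁵ + (1 − s)⁵ = 0.088, 0.170, 0.328 and 0.590.

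A second set-up let each physician's pattern tendency vary continuously and correlate at 0.5 to 0.8 with that physician's outcome level (outcome ICC 0.05 to 0.20, pattern ICC 0.1 to 0.3). Ordinary regression gave a false effect of 0.06 to 0.37 SD and rejected 5.8% to 26.0% of the time. Fixed effects gave about 0 and 4.8% to 5.4%.

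**2. Type I error when physician habit and physician outcome level are unrelated.** The design effect for a regression slope is

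DEFF = 1 + (5 − 1) × ICC(outcome) × ICC(pattern), with true α = 2[1 − Φ(1.96/√DEFF)].

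At ICCs of 0.20 and 0.50, DEFF = 1 + 4 × 0.20 × 0.50 = 1.40 and α = 0.098. Over pattern ICC 0.1 to 0.5, α is 0.052–0.062 at outcome ICC 0.05, 0.055–0.074 at 0.10 and 0.059–0.098 at 0.20.

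Simulated rejection rates for ordinary regression (10 × 5 patients, overall F-test, 70% share, 6,000 runs, Monte Carlo error about 0.3 points):

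| Patterns | ICC 0 | 0.05 | 0.1 | 0.2 | 0.3 |
|---|---|---|---|---|---|
| 2 | 5.3% | 5.7% | 5.8% | 6.6% | 7.8% |
| 3 | 5.1% | 5.6% | 7.0% | 8.5% | 10.6% |
| 4 | 5.3% | 6.2% | 7.6% | 10.1% | 13.3% |

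At a 50% share the rate is about 5–7%. If pattern does not cluster by physician it is 4.6–5.4%. Fixed effects stay at 4.5–5.7% throughout.

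For a single contrast at a 70% share and ICC 0.1 or 0.3, with equal or unequal recruitment per physician, ordinary regression rejected 5.7–11.0% of the time. A random intercept with Satterthwaite degrees of freedom rejected 5.2–6.0%.

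**3. Precision of the ICC.** For an estimate of 0.2, F = (1 + 4 × 0.2)/(1 − 0.2) = 2.25 on 9 and 40 degrees of freedom. The exact 95% interval is about −0.02 to 0.58.

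**The case against.** The omission itself is not in dispute; its importance is.

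- **Status.** This is a pilot, the qualitative part has priority, Phase 2 is correlational, no significance level is set, and the plan disclaims testing the whole theory. This stands and limits the impact. The planned use for sizing later studies still remains.
- **Target.** If style is part of the exposure, variation between physicians is partly the thing studied, and an unadjusted association is a legitimate description. This stands in part: fixed effects answer a narrower, within-physician question. It is a reason to show both estimates, not to leave them undistinguished.
- **Noise.** With two groups of 25, the standard error is √(1/25 + 1/25) ≈ 0.28 SD, larger than a bias of 0.08 to 0.20 SD. True, but the bias does not average out as such data accumulate.
- **Assumptions.** ICC, gap and share are all assumed. The simulations give each visit one pattern, while the plan allows combinations. The degree of physician control is judged on the two patterns described in Step 6, since the definitions in Table 1 were not in the available text. All of this stands.
- **Remedy.** The random intercept leaves about 59–82% of the bias (0.062/0.105 to 0.339/0.412). This stands, and is why fixed effects must be reported beside it.
- **Scope.** Symptom severity is the weakest case, as it would cluster mainly through case mix. Congruence, which uses the physician's own rating, has the same omission.

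**Conclusion.** The concern holds. As written, the plan analyses patients nested in physicians with models that ignore the physician, while the explanatory variable is partly physician behaviour. Confounding is the larger problem: with a 0.5 SD gap, a false pattern difference of 0.10 to 0.40 SD at habitual shares of 60% to 90%. Understated p-values are the smaller one: about 6% at ICC 0.05, up to 8–13% at ICC 0.3 with a 70% share. Neither arises if pattern does not cluster by physician, or if the outcome does not. The case is strongest for satisfaction and PEPPI-10. Since the size depends on quantities the documents do not give, confidence is medium; the fix is still worth making because it is cheap and the data can show whether the problem is present.

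**What to change.** For the continuous patient-reported variables, above all satisfaction and PEPPI-10:

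1. Group patterns into a few categories, which the dummy-coding sentence permits.
2. Replace ordinary linear regression with a model that has a random intercept for physician and Satterthwaite or Kenward-Roger degrees of freedom.
3. Report a physician fixed-effects estimate beside it, as the check on confounding between physicians.
4. Report the number of patients and of patterns per physician, and the physician ICC with its interval, described as an imprecise planning value.

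For binary congruence, keep the planned logistic regression, state that clustering by physician is not accounted for, and interpret it cautiously.

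**Cost.** Analysis wording only; physician identity is already known. Fixed effects use 9 degrees of freedom (48 to 39 with two patterns; 42 to 33 with all eight) and raise the standard error by about 4, 11, 25 and 70% at shares of 60, 70, 80 and 90%. Physicians seen with one pattern only add nothing to that estimate, so the check is weakest where habit is strongest.
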